### 5.6 PAL™ Battery Charger

The battery charger (Figure 11) can charge up to four batteries at a time.

A green indicator light in the center of the charger confirms that the charger is properly connected to electrical power. Each battery slides into a bay to connect to the battery charger. Each bay has an indicator light to show the battery charging status. It takes approximately three hours to charge a Single Battery and five hours to charge a Dual Battery, depending on the degree of battery depletion. It is safe to leave the batteries in the charger and the charger plugged into a wall outlet at all times.

[figure not shown]

Figure 11: Pal™ Battery Charger (Red Arrows indicate Battery Charging Status Lights; Orange Arrow indicates Power Indicator Light)

Battery Charging Status Light	What it Means
Green	Battery is fully charged and ready for use.
Yellow	Battery being charged; NOT ready for use.
<Flashing> Yellow	Battery NOT charging. Check battery connections. If connections are intact, switch to another battery slot. If problem persists, return battery to HeartWare.
Red	Battery too cold or too hot; waiting to charge.
<Flashing> Red	Defective battery. Do NOT use. Mark battery and return to HeartWare.

**5.7 PAL™ Controller AC Adapter or DC Adapter**

**5.7.1 AC Adapter**

The AC adapter (Figure 12) connects the controller to a wall electrical outlet. When the AC adapter is properly connected to power, a blue indicator light will be displayed on the adapter. When connected to the controller via the YELLOW port, it supplies power to the controller and pump and charges both the controller internal and external batteries. If the controller is connected to the AC power source when both batteries are depleted, the internal battery will charge first. After the internal battery is completely charged, the external battery will charge.

When using the AC or DC adapter with no external battery attached, be sure to always place the Pal Cap on the Pal Controller.

Before connecting the AC adapter to the controller, verify proper connection of the power cord to the adapter (Figure 12) and electrical outlet.

**Figure 12: AC adapter & Power cord connection**

**5.7.2 DC Adapter**

The DC adapter (Figure 13) is used to provide power to the controller and pump from a vehicle power port. When connected to a running vehicle, it will power the controller and charge both the internal and external battery. The charge sequence for both batteries is the same as that of the AC adapter. When the DC adapter is properly connected to power, a blue indicator light will be displayed on the adapter.

**Figure 13: DC adapter**

### **5.8 Device Accountability**

The MVAD Pump and components are investigational devices. The Investigator is responsible for ensuring that only study participants utilize the MVAD Pump, and all MVAD Systems must be stored in a location that is accessible only by authorized personnel. The disposition of all MVAD components must be maintained by serial number or lot number and must be accounted for in the Device Accountability Log. All unused product will be returned to HeartWare.

## **6.0 STUDY OBJECTIVES AND ENDPOINT MEASURES (ENDPOINTS)**

### **6.1 Study Objectives**

This multi-center, prospective, non-randomized, single-arm trial will investigate the safety and performance of the HeartWare Miniaturized Ventricular Assist Device (MVAD Pump) system over 24 months in subjects with advanced heart failure. Secondary endpoints include the incidence of bleeding, incidence of major infections (per INTERMACS definitions), time to death, incidence of all device failures and device malfunctions, health status improvement, and functional status improvement. Safety measures will include the frequency and rates of adverse events, both overall and for each specific event, which will be collected throughout MVAD Pump support.

This is a performance goal based trial concerning the primary endpoint and the first secondary endpoint. The primary endpoint is survival at 6 months (estimated to be 85%) based on a performance goal of 70%, with a one-sided significance level of 0.05. The initial Clinical Study Report will be submitted with the 6 month data and will be submitted for CE Mark. The secondary endpoint is survival at 24 months (estimated to be 70%) based on a performance goal of 52.5%, with a one-sided significance level of 0.05. These data will be submitted for long term use labeling.

### **6.2 Estimated Period of Trial**

#### **6.2.1 Time schedule**

Enrollment of subjects is expected to start in the second quarter of 2015 (First Implant) and each subject will be in the trial for up to 24 month (including Screening and Follow-up phases).

#### **6.2.2 End of trial**

Enrollment of subjects is expected to be completed in the fourth quarter of 2015 (Last Implant) and the overall end of trial is defined as the day of the last visit performed on the last subject. The last Follow-up visit of the last subject is expected to take place by the fourth quarter of 2017.

### **6.3 Primary Endpoint**

The primary endpoint is survival at 6 months presented as a simple proportion (subjects alive on the MVAD pump divided by endpoint eligible subjects). Transplants, explants for recovery and exchanges (to a device other than the MVAD Pump) prior to 6 month follow-up will be eligible for endpoint analysis (with survival status identified at the time of the procedure). Survival failure is associated with events (death) on the MVAD Pump.

#### 6.4 Secondary Endpoints

1. Survival at 24 months presented as a simple proportion (defined like the primary endpoint)
2. Overall Survival (Time to Death)
3. Incidence of major bleeding, per INTERMACS definition
4. Incidence of all device failures and device malfunctions per INTERMACS definition
5. Incidence of major infection, per INTERMACS definition
6. Incidence of neurological dysfunction per INTERMACS definition
7. Health Status change, as measured by Kansas City Cardiomyopathy Questionnaire (KCCQ) and EuroQol EQ-5D-5L
8. Functional status change, as measured by NYHA and 6-minute walk
9. Frequency and rates of adverse events(AEs) throughout VAD support per INTERMACS Definition
10. Length of operative time and initial hospital stay
11. Re-Hospitalizations(excluding planned procedures)
12. Transplantations
13. Explants

## **7.0 STUDY DESIGN**

### **7.1 Number of Clinical Sites and Subjects**

The trial will be conducted at a minimum of 5 sites and a maximum of ten (10) sites in up to 5 countries, including Germany, Austria, France, United Kingdom (UK), and Australia.

Screening will be continued until 60 subjects are implanted.

It is anticipated that each site will enroll up to 10 subjects but at least 1 subject each. No site will enroll more than 10 subjects into the study without prior written approval from HeartWare.

### **7.2 Subject Participation and Study Duration**

Subjects will participate for 24 months.

All subjects will be followed for 6 months to the primary endpoint, and will continue until assessment at 24 months for the key secondary endpoint.

The study is anticipated to start in the Second Quarter 2015 (First Implant) and enrollment is estimated to be complete by Fourth Quarter 2015 (Last Implant) to Fourth Quarter 2017 (Last subject last visit).

### **7.3 Site Selection Criteria**

Factors determining whether centers will be selected include the number and kinds (e.g. continuous flow) of VAD implants per year, the infrastructure necessary to perform this trial, in particular having the core surgical and cardiology VAD teams and an established research group structure. The center's interest in participating in the trial, their academic history and geographic location will all be taken into consideration. In addition, sites need to adhere to all trial-related requirements, to Good Clinical Practice (GCP), ISO 14155 2011 and to all applicable regulatory rules and regulations.

## **8.0 PATIENT POPULATION, SELECTION AND WITHDRAWAL**

### **8.1 Characterization of Study Population**

The study population will be selected from patients with American Heart Association (AHA) Stage D/NYHA Class IIIB/IV heart failure who have failed optimal medical management. Candidates will be selected for the study regardless of gender, race or ethnicity.

Prior to enrollment, candidates must meet all the inclusion criteria, and none of the exclusion criteria.

#### **8.1.1 AHA Stage D, NYHA Class IIIB/IV Heart Failure**

The distinction between NYHA Class III versus IV heart failure is primarily based upon the presence or absence of symptoms of failure at rest. A Class III patient experiences dyspnea with activities of daily living or walking short distances (20-100 m). Class IIIB patients may not be able to walk >300 meters, and experience some symptoms at rest. Physical measures such as PVO2, neuro-hormonal levels and LVEF do not provide sufficient resolution to differentiate a later stage Class IIIB patient from a Class IV, although tools such as the Seattle Heart Failure Score appear to be better for stratifying risk of death in patients defined as IIIB or IV. However, a formerly stable NYHA IIIB patient may transition to Class IV by the gradual development of symptoms at rest or by failure of optimal medical management. In the former case, transitional symptoms would be the development of paroxysmal nocturnal dyspnea, increasing orthopnea, reduction in tolerance to exercise and the occurrence of symptoms at rest, all of this occurring on previously stable and optimal medical management.

### 8.1.2 Definition of Optimal Medical Management (OMM)

Optimal medical management is defined as dietary salt restriction and *maximal tolerable therapy* with:

- Angiotensin Converting Enzyme (ACE) Inhibitors (or Angiotensin Receptor Blockers (ARBs))
- Diuretics
- Beta Blockers
- Aldosterone Antagonists

Many patients will also receive cardiac glycosides and hydralazine/nitrates. In addition, therapy with Cardiac Resynchronization Therapy (CRT), use of anti-arrhythmic agents and an Implantable Cardiac Defibrillator (ICD) may be expected in many Stage D/NYHA Class III/IV patients.

Intermittent or continuous therapy with inotropic agents may be required or have been used in this patient population. Enrollment, however, does not require concurrent intravenous inotropes, provided criteria for Stage D/NYHA Class III/IV are met.

Failure of optimal medical management is defined as:

- Development of symptoms at rest and reduction in exercise tolerance in previously stable III/IV patients who have received maximally tolerable doses of the four major categories of drugs and are not candidates for, or improved by, CRT.
- Development of drug intolerance in a previously stable III/IV patient due to hypersensitivity (e.g. ACE inhibitors or ARBs), hypotension (e.g. ACE inhibitors, ARBs or beta blockers) or renal impairment (e.g. ACE inhibitors, aldosterone antagonists) resulting in development of some symptoms at rest despite alternative drug therapy.
- Occurrence of pulmonary congestion, ascites or refractory peripheral edema despite maximal tolerable medical therapy in Class IV patients.
- Necessity for intermittent or continuous IV inotropes, intra-aortic balloon pump or hospitalization for heart failure in either Class III/IV patients who have failed maximal tolerable medical therapy or who developed sensitivity to any of the classes of drugs.

## 8.2 Inclusion Criteria

1. Must be  $\geq 18$  years of age at consent
2. Subjects with advanced heart failure symptoms (Class IIIB or IV) who meet one of the following):
  - a. on optimal medical management including dietary salt restriction and diuretics, for at least 45 out of the last 60 days and are failing to respond;  
or
  - b. in Class III or Class IV heart failure for at least 14 days and dependent on intra-aortic balloon pump (IABP) and/or inotropes.
3. Left ventricular ejection fraction  $\leq 25\%$ .
4. Female subjects of childbearing potential must agree to use adequate contraceptive precautions (defined as oral contraceptives, intrauterine devices, surgical contraceptives or a combination of condom and spermicide) for the duration of the study.
5. The subject has signed the informed consent form (ICF).

## 8.3 Exclusion Criteria

1. Body Mass Index (BMI)  $> 47$ .
2. Body Surface Area (BSA)  $< 1.0 \text{ m}^2$ .
3. Partial or full mechanical circulatory support within thirty days of implant.
4. Existence of any ongoing mechanical circulatory support (MCS) other than an intra-aortic balloon pump (IABP) or TandemHeart PTVA .
5. Prior cardiac transplant or cardiomyoplasty.
6. History of confirmed, untreated abdominal or thoracic aortic aneurysm  $> 5 \text{ cm}$ .
7. Acute myocardial infarction within 14 days of implant as diagnosed by ST or T wave changes on ECG, diagnostic biomarkers, ongoing pain and hemodynamic abnormalities.
8. On ventilator support for  $> 72$  hours within the four days immediately prior to implant.
9. Pulmonary embolus within three weeks of implant as documented by computed tomography (CT) scan or nuclear scan.
10. Symptomatic cerebrovascular disease, stroke within 180 days of implant or  $> 80\%$  stenosis of carotid or cranial vessels in the absence of confirmed collateral circulation.
11. Uncorrected moderate to severe aortic insufficiency.
12. Severe right ventricular failure as defined by the anticipated need for extracorporeal membrane oxygenation (ECMO) or BiVAD at the time of screening.

13. Active, uncontrolled infection diagnosed by a combination of clinical symptoms and laboratory testing, including but not limited to, continued positive cultures, elevated temperature and white blood cell (WBC) count, hypotension, tachycardia, generalized malaise despite appropriate antibiotic, antiviral or antifungal treatment.
14. Uncorrected thrombocytopenia or generalized coagulopathy (e.g., platelet count <75,000, INR >2.0 or PTT >2.5 times control in the absence of anticoagulation therapy).
15. Intolerance to anticoagulant or antiplatelet therapies or any other peri- or postoperative therapy that the investigator may administer based upon the subject's health status.
16. Serum creatinine >3.0 mg/dL within 72 hours of implant or requiring dialysis.
17. Specific liver enzymes [AST (SGOT), and ALT (SGPT)] >3 times upper limit of normal within 72 hours of implant.
18. A total bilirubin >3 mg/dL within 72 hours of implant, or biopsy proven liver cirrhosis or portal hypertension.
19. Pulmonary vascular resistance (PVR) is demonstrated to be unresponsive to pharmacological manipulation.
20. Subjects with a mechanical heart valve.
21. Etiology of heart failure is due to, or associated with, uncorrected thyroid disease, obstructive cardiomyopathy, pericardial disease, amyloidosis, active myocarditis or restrictive cardiomyopathy.
22. History of severe chronic obstructive pulmonary disease (COPD) or severe restrictive lung disease (e.g. forced expiratory volume in one second (FEV1) < 50% predicted value).
23. Participation in any other trial involving investigational drugs or devices within 4 weeks prior to screening and last visit of the trial.
24. Severe illness, other than heart disease, which would limit survival to <3 years.
25. Peripheral vascular disease with rest pain or ischemic ulcers of the extremities.
26. Pregnancy and breastfeeding.
27. Psychiatric disease, irreversible cognitive dysfunction or psychosocial issues that are likely to impair compliance with the CIP and LVAD.
28. Subject unwilling or unable to comply with trial requirements.
29. Technical obstacles, which pose an inordinately high surgical risk, in the judgment of the investigator.
30. Employees of the investigator or trial site, with direct involvement in this trial or other trials under the direction of the investigator or trial site, as well as family members or employees of the Investigator.

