**Main Criteria for Inclusion:**

1. Must be  $\geq 18$  years of age at consent
2. Subjects with advanced heart failure symptoms (Class IIIb or IV) who meet one of the following):
  - a. on optimal medical management including dietary salt restriction and diuretics, for at least 45 out of the last 60 days and are failing to respond; or
  - b. in Class III or Class IV heart failure for at least 14 days and dependent on intra-aortic balloon pump (IABP) and/or inotropes.
3. Left ventricular ejection fraction  $\leq 25\%$ .
4. Female subjects of childbearing potential must agree to use adequate contraceptive precautions (defined as oral contraceptives, intrauterine devices, surgical contraceptives or a combination of condom and spermicide) for the duration of the study.
5. The subject has signed the informed consent form.

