**Main Criteria for Exclusion:**

1. Body Mass Index (BMI) > 47.
2. Body Surface Area (BSA) < 1.0 m^2.
3. Partial or full mechanical circulatory support within thirty days of implant.
4. Existence of any ongoing mechanical circulatory support (MCS) other than an intra-aortic balloon pump (IABP) or TandemHeart PTVA .
5. Prior cardiac transplant or cardiomyoplasty.
6. History of confirmed, untreated abdominal or thoracic aortic aneurysm (diameter > 5 cm).
7. Acute myocardial infarction within 14 days of implant as diagnosed by ST or T wave changes on the electrocardiogram (ECG), diagnostic biomarkers, ongoing pain and hemodynamic abnormalities.
8. On ventilator support for > 72 hours within the four days immediately prior to implant.
9. Pulmonary embolus within three weeks of implant as documented by computed tomography (CT) scan or nuclear scan.
10. Symptomatic cerebrovascular disease, stroke within 180 days of implant or > 80% stenosis of carotid or cranial vessels in the absence of confirmed collateral circulation
11. Uncorrected moderate to severe aortic insufficiency.
12. Severe right ventricular failure as defined by the anticipated need for extracorporeal membrane oxygenation (ECMO) at the time of screening.
13. Active, uncontrolled infection diagnosed by a combination of clinical symptoms and laboratory testing, including but not limited to, continued positive cultures, elevated temperature and white blood cell (WBC) count, hypotension, tachycardia, generalized malaise despite appropriate antibiotic, antiviral or antifungal treatment.
14. Uncorrected thrombocytopenia or generalized coagulopathy (e.g., platelet count < 75,000, International Normalized Ratio (INR) > 2.0 or Partial Thromboplastin Time (PTT) > 2.5 times control in the absence of anticoagulation therapy).
15. Intolerance to anticoagulant or antiplatelet therapies or any other peri- or postoperative therapy that the investigator may administer based upon the subject's health status.
16. Serum creatinine > 3.0 mg/dL within 72 hours of implant or requiring dialysis.
17. Specific liver enzymes [Aspartate Aminotransferase (AST) (SGOT), and Alanine Aminotransferase (ALT) (SGPT)] > 3 times upper limit of normal within 72 hours of implant.
18. A total bilirubin > 3 mg/dL within 72 hours of implant, or biopsy proven liver cirrhosis or portal hypertension.
19. Pulmonary vascular resistance (PVR) is demonstrated to be unresponsive to pharmacological manipulation.

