### 9.1.4.2 Cardiovascular/ Medical history & Hospitalization

Medical history will be collected and recorded for all subjects enrolled in the trial. This includes diagnosis, general medical history and cardiovascular history as follows:

- General medical history
- Primary cardiac diagnosis
- Previous cardiac surgery
- Current mechanical support (ECMO, balloon pump)
- Previous mechanical circulation support
- Etiology of Heart Failure
- Duration of Heart Failure
- Number of hospitalizations in past year for cardiac
- Smoking

With co-morbidities to be identified as

- Diabetes (diet, oral, insulin)
- COPD
- Previous neurological event
- Carotid artery disease
- Peripheral vascular disease
- Arterial Fibrillation
- NYHA class

Childhood illnesses, unless considered to be relevant to the etiology of heart failure, do not need to be documented.

**9.1.5 Hemodynamic parameters/ Vital Signs & Improved Blood Pressure Management Plan (IBPM)****9.1.5.1 Hemodynamic parameters/ Vital Signs**

Hemodynamic parameters will include the following, which will be captured at screening/ pre-implant, day 1-3, and month 1, 3, 6, 12, 18, 24, and re-hospitalization (where applicable):

	Screening	Day 1-3 post implant	Month 1, 3, 6, 12, 18, 24
Heart Rate/ Rhythm	x	x	x
Respiratory Rate	x	x	x
Temperature	x	x	x
Systolic blood pressure	x	x	x 
Diastolic blood pressure	x	x	x 
Mean Arterial Blood Pressure (MAP) 	x	x	x 
Doppler - Pressure	x	x	x 
Central venous pressure 	x		
SVO 2	x	x*	x*
Right atrial pressure 	x		
Systolic pulmonary artery pressure 	x		
Diastolic pulmonary artery pressure 	x		
Mean pulmonary artery pressure 	x		
PCWP	x		
Cardiac Index	x		
Cardiac output	x		
PVR 	x		

\*if available

 follow IBPM program (Section 9.1.5.2) as applicable

 After screening only to be collected in case of late Right Heart Failure

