#### **14.6.1.3 CIP Deviations and Medical Emergencies**

The Investigator will not deviate from the CIP without the prior written approval of HeartWare except in medical emergencies or in unforeseen, isolated instances where minor changes are made that will not increase the subject's risk or affect the validity of the study. In addition HeartWare will not allow any deviations/waiver from the Inclusion and Exclusion Criteria.

In medical emergencies, prior written approval for CIP deviations will not be required, but HeartWare personnel must be notified via telephone within 24 hours of occurrence.

If there are any circumstances during the clinical trial which can affect the safety of the subjects, users or third person, HeartWare and the investigator will take all necessary security measures immediately to protect the subjects, users and third persons against direct or indirect risk. HeartWare and the investigator have to inform the CA and the responsible IEC immediately about these new circumstances and the measures taken.

However in case of any deviation for a scheduled assessment e.g. out of window assessment, missing laboratory sample, and prior approval from HeartWare is required in advance for changes in or deviations from the CIP.

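### Does exclusion 3 shut out the balloon-pump patients whom inclusion 2b recruits?

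*Protocol*

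**What the plan says.** Three criteria bear on the point. Each reads the same in the protocol synopsis (section 2.0) and in the body (sections 8.2 and 8.3).

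- Inclusion 2b admits patients "in Class III or Class IV heart failure for at least 14 days and dependent on intra-aortic balloon pump (IABP) and/or inotropes".
- Exclusion 3 bars "Partial or full mechanical circulatory support within thirty days of implant".
- Exclusion 4 bars "Existence of any ongoing mechanical circulatory support (MCS) other than an intra-aortic balloon pump (IABP) or TandemHeart PTVA".

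Section 8.1 makes the criteria joint: "candidates must meet all the inclusion criteria, and none of the exclusion criteria". Section 14.6.1.3 rules out case-by-case relief: "HeartWare will not allow any deviations/waiver from the Inclusion and Exclusion Criteria". Section 8.1.2 counts the need for a balloon pump among the ways in which optimal medical management can fail. The history list in section 9.1.4.2 has one entry for "Current mechanical support (ECMO, balloon pump" and another for "Previous mechanical circulation support". The abbreviation list expands MCS, but no section defines partial or full support.

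**The concern.** Exclusion 4 carves IABP and TandemHeart out of a rule about mechanical circulatory support, so the protocol itself treats both as such support. A patient with a balloon pump running at implant has therefore had mechanical support inside the thirty-day window. Exclusion 3 has no carve-out, one met exclusion is enough to bar a candidate, and waivers are refused. Followed to the letter, the IABP route of inclusion 2b and both exceptions in exclusion 4 would admit nobody.

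If sites read the line differently, the same patient could be enrolled at one centre and turned away at another, and the enrolled patient might or might not be listed as an eligibility deviation. The mix of patients behind a single-arm comparison with fixed performance goals would then depend partly on how each site read one sentence.

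**Working it through.** No stated figure depends on this point, so the check consists of laying the criteria against each kind of patient. The literal reading takes exclusion 3 to cover any support in the thirty days, running or ended. The divided reading takes exclusion 3 to cover earlier, ended support and exclusion 4 to cover support still running. Each patient is assumed otherwise eligible.

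| Patient | Literal reading | Divided reading |
|---|---|---|
| IABP running at implant | Excluded by 3, though 2b and 4 allow it | Eligible |
| TandemHeart running at implant | Excluded by 3, though 4 allows it | Eligible |
| Other mechanical support running at implant | Excluded by 3 and 4 | Excluded by 4 |
| IABP or TandemHeart removed within thirty days | Excluded by 3 | Excluded by 3 |
| Inotropes only, no mechanical support in thirty days | Eligible | Eligible |

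**What is open.** Only the first two rows change. Inotrope-only entry under 2b is unaffected, and recently removed support is excluded on both readings.

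**Which reading the text supports.** On the literal reading, any patient whom exclusion 4 bars is already barred by exclusion 3, because support running at implant falls within the thirty days. Exclusion 4 would then add nothing, its exceptions could never operate, and the IABP words in 2b would be dead. On the divided reading each provision has a function. Inclusion 2b, exclusion 4 and section 8.1.2 all place balloon-pump patients within the population sought. The separate history entries for current and previous support fit this reading but add little: the first entry also names ECMO, which exclusion 4 bars when ongoing, so that list does not track eligibility.

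**What would change in the analysis.**

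1. Protocol section 12.2 defines the ITT population by enrolment and intention to implant at skin incision. SAP 8.3.2 defines it by consent and anaesthesia for implantation. The per-protocol population (protocol 12.2, SAP 8.3.3) is the ITT subjects who received the pump. None of these definitions removes an enrolled subject for an eligibility deviation, so reclassifying one moves nobody into or out of the 6-month or 24-month survival proportion.
2. SAP 5.2 records an early stop with fewer than 15 subjects enrolled, against 60 planned, and replaces summary statistics with case studies.
3. What remains is the deviation listing. SAP 8.2 has the sponsor's review team set the categories, review the listing and approve each determination before the database closes.

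**The case for a change.** The strongest reply is that the divided reading is an inference. Exclusion 4 shows that the drafters could write a word meaning still in progress; exclusion 3 has no counterpart. A pre-implant window does not by itself imply that support has ended: exclusion 8, "On ventilator support for > 72 hours within the four days immediately prior to implant", on its face takes in ventilation still running at implant. A further reading, carrying the IABP and TandemHeart exception over into exclusion 3, would also remove the conflict and would make a patient with recently removed support eligible. The divided reading has an odd result too: a patient taken off a balloon pump within the thirty days is out, while one still on it is in. And with reporting now by individual case, a per-subject deviation listing matters more than it would in a table of 60.

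Part of this stands. The scope of exclusion 3 is not written down, and a clarifying phrase would do no harm. The rest carries less weight.

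- Exclusion 8 is a duration rule with no companion criterion on ongoing ventilation; exclusion 3 has such a companion in the next line. Exclusions 7, 9 and 10 use the closer form of words (within 14 days, three weeks and 180 days of implant) for infarction, embolus and stroke, which are earlier events. Neither comparison proves the scope.
- Carrying the exception into exclusion 3 needs words that are not there. For support running at implant, it gives the same answer as the divided reading.
- The contrast between removed and continuing support questions the merit of an eligibility rule, on which no view is taken here. It is not a contradiction in the text.
- The listing matters only if such a subject exists. The documents do not show that one was enrolled or that sites differed. Section 9.1.4.2 already collects current and previous support, so a case study can show the facts, although the protocol does not say whether removal dates are recorded.

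**Conclusion.** No change to the plan follows. This is a gap in wording that sites and the deviation review team can close sensibly from the adjacent, more specific criteria. Writing the reading down would tidy the text without altering any result.

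The open question is confined to patients with IABP or TandemHeart support running at implant. The effect on sample size, power, the performance-goal tests and the membership of the analysis populations is nil as the documents define them. The remaining consequence is at most the label on such a subject in the deviation listing, within a trial that stopped with fewer than 15 enrolled.

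This rests on two assumptions: that sites read exclusions 3 and 4 together with inclusion 2b rather than exclusion 3 alone, and that the review process in SAP 8.2 was applied to whoever was enrolled. The documents cannot confirm either, but nothing in them points the other way.
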